We hypothesize that the addition of the Osto-Ring™ will reduce leakage from the stoma appliance and may also increase the length of time needed between pouch changes. Currently, the mean ostomy pouch wear time in the United States is 5.2 days (Richbourg L, Fellows J, Arroyave WD. Ostomy pouch wear time in the United States. *J Wound Ostomy Continence Nurs.* 2008 Sep-Oct;35(5):504-8), and out-of-pocket costs can be as high as \$30 with each pouching system change which translates to a yearly cost of close to \$3000. Longer wear time would therefore translate into needing fewer ostomy bags and less money spent on ostomy supplies.

Overall Objective:

The primary objective of this pre-market study is to assess the safety and performance of the Osto Ring™ as it relates to the pouching system wear time and degree of leakage.

Protocol Version #1
Dated 4/22/19

Research Design:

Study population: 30 adult subjects who have had an ileostomy or colostomy for at least 6 months, who currently use the Hollister New Image 2 piece pouching system acting as their own controls, will use their standard 2 piece New Image Hollister pouching system without the Osto Ring™ for 28 days. On Day 29 subjects will be switched to the Osto-Ring regimen until day 56. Patients will be evaluated in person at Day 0 and approximately Days 28, 56, and 75 (within business days and scheduling convenience).

The Osto-Ring for this study is being supplied by GoDuRn, LCC, and provided to subjects free of charge.

During the standard of care visit to the health care provider, subjects will be evaluated to confirm that they meet the criteria for participating in this study.

Study Design:

Day 0-27

Visit One

- **Subject will wear their standard of care Hollister 2 piece New Image pouching system for 28 days.**
 - At the first visit they will remove their pouching system to allow the investigator to assess their skin (research staff will take photo) using the Ostomy Skin Tool Reference Guide [See appendix B]
 - They will be given and asked to fill out the Quality of Life Questionnaire [See appendix C]
 - They will be given Ostomy Evaluation Record [See appendix A] and asked to complete this at every pouching system change. (And take photos of the skin site and adhesive side of the ostomy flange.)

Day 28-55

Visit Two

- **Subjects will now wear their standard of care Hollister 2 piece New Image pouching system with the Osto-Ring for the next 28 days.**

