 - At the first visit they will remove their pouching system to allow the investigator to assess their skin using the Ostomy Skin Tool Reference Guide [see appendix B] (photo taken)
 - They will be fitted for the proper Osto-Ring size and given a belt.
 - They will be given and asked to fill out the Quality of Life Questionnaire [See appendix C]
 - They will be given 2 questionnaires and asked to complete them at every pouching system change. Subject will take photograph at each stoma change
 - Ostomy Evaluation Record [See appendix A]
 - Osto Ring Evaluation Record [See appendix D]

Day 56

Visit Three

Patients will decide if they want to continue using the Osto-Ring™ with their standard of care pouching system.

- Their pouching system will be removed and will have a skin assessment by the investigator using the Ostomy Skin Tool Reference Guide, Appendix B.

Protocol Version #1

Dated 4/22/19

- They will be asked how they are doing and to report any side effects they may have experienced even if they do not think it is related to the Osto-Ring™.
- They will be asked to complete :
 - The Ostomy Quality of Life Questionnaire

If they felt that the Osto Ring was helpful, subjects will be asked to extend the wear of their devices by 1-4 days per their experience (if possible). Photographs will be taken at each stoma change of the skin and the adhesive side of the flange.

Day 75

Visit Four

At this last visit, patients can decide to have their Osto Ring removed or continue using it if they like.

All four of the clinic visits are considered research-related, along with completion of questionnaires and peristomal skin assessment.

During this study, [name] and his research team will collect information about the patients for the purposes of this research. This includes their name, telephone number, medical record number, initials, date of birth, medical, surgical and medication history, date of study entry, dates of study procedures and results of tests and procedures done as part of the study.

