9. Assessed with an ostomy skin tool score of ≥ 3

Primary Outcomes:

Performance Efficacy:

To evaluate the Osto Ring™ for pouching system wear time, and degree of leakage in subjects when using the Osto Ring™ as compared to when not using the Osto-Ring™

- Integrity of the adhesive side of the flange (photos)
- Wear Time:
 - Total time pouching system worn will be calculated by the Ostomy Evaluation Record. This is defined as the difference between the dates and times the appliance is changed. (Appendix A)
- Leakage:
 - Degree of leakage at time of pouching system changes will be measured using line item from Ostomy Evaluation Record (Appendix A)

Secondary Outcomes:

1. The condition of the peristomal skin and stoma (Appendix B)
2. The number and frequency of adverse events
3. The subjects' quality of life using the Stoma Quality of Life (QoL) questionnaire (Appendix C)
4. Subject Ease of Use (ease of application, pain level with application, comfort, convenience of use) will be assessed using Likert scale: 1 = poor, 2 = satisfactory 3= very good, 4= excellent (Appendix D)

Analysis plan:

Protocol Version #1

Dated 4/22/19

All means and frequencies will be compared between the groups with the Osto Ring™ versus the group without it and will be controlled for the order in which a subject used the Osto Ring.

- Wear Time:
 - Mean days in between pouching system changes
- Leakage:
 - Frequency of any degree of leakage at pouching system changes
 - Frequency of much leakage at time of pouching system change
- Skin condition:
 - % of patients with moderate to severe skin conditions at time of each WOC nurse or physician study visit
 - Mean % of time with moderate to severe skin conditions throughout the 4 week interval at every WOC nurse or physician study visit
- Quality of Life:
 - Mean quality of life scores
- Time per Ostomy Care Session
 - Mean minutes spent during ostomy care session
- Ease of Use
- Mean % of time ease of use reported as very good or excellent by subject , Satisfaction and Confidence
 - Mean satisfaction and confidence scores
- Device Recommendation
 - % of subjects reporting they strongly agree to recommend the device to others

We will compare the baseline characteristics of the two groups. Continuous variables will be compared with the paired *t* test, and categorical variables were compared with the Fisher exact test. Each item on the ostomy evaluation record form will be individually reported.

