Safety Assessments and Termination Guidelines

WOC nurses will perform skin assessments at key times. Patients are to be told that they must mention any deviation from their baseline ostomy pouching system changing routine. Failure to do so will result in a protocol violation. Patients receiving an Ostomy Skin Tool score of ≥ 3 without a known cause will be withdrawn from the study.

Any patient suffering an allergic reaction to either product (the standards New Image Hollister appliance or Osto Ring) or suspected of having an adverse reaction of any kind as determined by the patient and/or the ostomy will be removed from the trial, return for clinical assessment as indicated and return to their standard stoma care appliance.

The data safety monitoring committee will consist of Drs [name] and [name], who will review any unanticipated adverse events and have the authority to stop the trial at any time if any safety concerns are raised.

Osto-Ring™ Risks

Side effects may include:

- allergic reaction to the ring,
- worsening of the peristomal skin condition, or
- prolonged time needed in changing the ostomy pouching device.

2-piece New Image Hollister Pouching System

The 2 piece New Image Hollister Pouching System is standard of care. Concerns regarding this system will be handled by the regular physician. However, all concerns will be addressed.

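### A suspected reaction ends trial participation as well as ring use, so subjects removed before Day 56 are missing from the ring-period skin and quality-of-life results and their reactions are not followed

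*Combined protocol and SAP*

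**What the plan says.** **The removal rule (Safety Assessments and Termination Guidelines).** It applies to an allergic reaction to either product, and to anyone "suspected of having an adverse reaction of any kind as determined by the patient and/or the ostomy". Such a subject "will be removed from the trial, return for clinical assessment as indicated and return to their standard stoma care appliance". Leaving the trial and going back to the usual appliance are stated as separate consequences. A neighbouring rule covers the skin score: "Patients receiving an Ostomy Skin Tool score of ≥ 3 without a known cause will be withdrawn from the study". It names no day.

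**The visits (Research Design and Study Design).** The general schedule is: "Patients will be evaluated in person at Day 0 and approximately Days 28, 56, and 75". The ring is fitted at Visit Two (Day 28). At Visit Three (Day 56) the listed procedures are a skin assessment ("Their pouching system will be removed and will have a skin assessment by the investigator using the Ostomy Skin Tool Reference Guide"), a side-effect question ("They will be asked how they are doing and to report any side effects they may have experienced") and the quality-of-life questionnaire. Visit Four (Day 75) lists only the choice of keeping or giving up the ring.

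**The outcomes.** Secondary Outcomes include peristomal skin condition, quality of life and "The number and frequency of adverse events". The Analysis plan summarises skin as a percentage of patients at study visits. It names no analysis set, no denominator and no handling of withdrawn subjects or missing data.

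**The concern.** The reason for leaving overlaps with what is being measured. The Osto-Ring risk list names allergic reaction and worsening peristomal skin. Either can trigger removal, and skin condition is also an outcome. A subject who does badly on the ring in Days 28 to 55 can therefore leave before the one listed assessment that would show it. The Day 56 skin and quality-of-life figures then describe those who remain, and the comparison with Day 28 leans toward the ring.

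The study would also be unable to say how long ring reactions lasted or whether they resolved, because no study record is specified after removal. Safety is part of the stated primary objective, so this is more than a side issue.

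**Working it through.** **1. The plan's own figures.** The plan gives no reaction or removal rate. The nearest stated figure is the sample size. The effect size is (6.26 − 5.01)/2.25 = 0.556, which the plan gives as 0.56. A two-sided paired t-test at 0.05 with n = 27 and d = 0.56 has power 0.7998, so the stated 27 reproduces. Enrolment is 30, a margin of 30 − 27 = 3.

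**2. What a subject removed between Days 28 and 55 leaves behind.**

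| Item | Source | Available? |
|---|---|---|
| Skin score and quality of life at Days 0 and 28 | Visits One and Two | Yes |
| Wear, leakage and yes/no skin item for each change before removal | Appendix A | Yes; the plan does not say whether they are kept in the analysis |
| The triggering reaction as an adverse event | Secondary Outcomes | Can be counted |
| Skin score at removal | None specified | No, only discretionary clinical assessment |
| Day 56 skin score, side-effect question, quality of life | Visit Three | No |
| Outcome of the reaction | None specified | No |

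The yes/no item in Appendix A does not replace the Ostomy Skin Tool score.

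**3. Effect on the Day 56 skin percentage.** Assume that r of 30 subjects are harmed and all are removed before Day 56, and that nobody else has skin damage. The visit shows 0/(30 − r), with exact upper 95% limit 1 − 0.025^(1/(30 − r)). The figure for everyone fitted is r/30 with Clopper-Pearson limits.

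- r = 3: 0/27, upper limit 1 − 0.025^(1/27) = 12.8%, against 3/30 = 10% (2.1% to 26.5%).
- r = 6: 0/24, upper limit 1 − 0.025^(1/24) = 14.2%, against 6/30 = 20% (7.7% to 38.6%).

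Both values of r are assumptions.

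**4. Wear time and leakage.** Inclusion criterion 6 requires at least two changes in seven days. At that pace, removal one week into ring wear leaves about two ring-period records. At the hoped-for 6.26 days it leaves about one. Most removed subjects could therefore still be paired, if their records are kept. If instead they supply no ring data, power at d = 0.56 is 0.80 with 27 pairs (3 removed) and 0.75 with 24 pairs (6 removed).

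**The case against.** The strongest reply is that harm is recorded in several places besides Visit Three.

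- The triggering reaction can be counted as an adverse event, and that outcome is not limited to completers. **This stands:** the occurrence of a reaction need not be lost.
- Each change brings a form with a skin item, a photograph and, in the ring period, a question on problems with the ring. **This stands for the period before removal.** It supplies neither an end-of-period score nor an outcome of the event.
- A reaction first found or reported at Day 56 is seen there. **This stands,** so the concern is limited to subjects removed earlier.
- Day 75 is also an in-person evaluation, and the protocol links skin assessment to the four visits in general terms. **This stands in part:** Visit Four lists no such procedure, and a subject already out of the trial would have no study reason to attend.
- The rule covers both products, so it can also remove subjects before Day 28. **This stands,** but such a subject never wears the ring and so gives no with/without pair. Inclusion criterion 3 requires at least 8 weeks on the standard system, which makes new reactions more plausible once the ring is added.
- The safety committee reviews events. Its stated remit is unanticipated adverse events, and the listed ring reactions are anticipated. **This does not close the gap.**

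A reader might go further and infer that nobody harmed by the ring is ever assessed, that every ring result comes from subjects who tolerated it, or that wear time is certainly biased toward the ring. The documents support none of these. Nothing in them discards records made before removal, and they give no wear-time change for removed subjects from which to size such a bias. Nor does the subject alone decide on removal: the text names a second decider, apparently with a word missing.

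**Conclusion.** The concern holds for the visit-based results. Followed as written, the rule selects the Day 56 skin and quality-of-life results toward subjects who tolerated the ring, and it leaves the course of ring reactions unrecorded. No analysis set or missing-data rule counters this.

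The size is unknown. At the assumed 10% to 20% removed, Day 56 could show no affected subjects when 3 to 6 of 30 were affected. That is the extreme case, in which every harmed subject leaves early and everyone else has clear skin. The direction rests on removed subjects having worse skin or quality of life than those who stay, which is plausible given what triggers removal.

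The effect on wear time, leakage and power is conditional on what happens to the earlier records. Whether and when the ring should be stopped is a clinical matter and is not judged here.

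**What to change.** In Safety Assessments and Termination Guidelines, separate stopping the study device from leaving the study. The decision to stop the device and the care that follows stay as they are. Then:

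1. Unless consent is withdrawn, keep the subject in follow-up at the scheduled Day 56 visit (skin score, side-effect question, quality of life) and record the outcome of the event at Day 75. Mark these values as taken off the ring, since skin may have changed since removal.
2. If the subject does return for clinical assessment, record the skin score then.
3. In the Analysis plan, keep all wear and leakage records up to removal in the ring period.
4. Beside the ring-period results, report the number removed for a reaction out of all subjects fitted with the ring.

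The cost is an amendment to the wording, contact with a few subjects who are off the device, and a short entry for event outcome, for which the appendices show no form. No additional scheduled visit is needed.

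### The committee that can stop the trial is not required to review the ring's listed harms or the withdrawals they lead to

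*Combined protocol and SAP*

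**What the plan says.** Under Safety Assessments and Termination Guidelines, the committee has two members "who will review any unanticipated adverse events and have the authority to stop the trial at any time if any safety concerns are raised". That sentence is the whole of its stated role.

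Under Osto-Ring Risks in the same section, the possible side effects include "allergic reaction to the ring" and "worsening of the peristomal skin condition", together with a longer time to change the appliance.

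Two rules act on the individual subject. For skin: "Patients receiving an Ostomy Skin Tool score of ≥ 3 without a known cause will be withdrawn from the study". A subject with an allergic reaction to either product, or a suspected adverse reaction of any kind, "will be removed from the trial, return for clinical assessment as indicated and return to their standard stoma care appliance".

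Elsewhere, Secondary Outcomes includes peristomal skin condition and adverse event counts, and Visit Three (Day 56) asks subjects about side effects whether or not they blame the ring.

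**The concern.** A committee with power to stop a trial adds something that subject-level rules cannot: it sees the pattern across subjects. Here its review duty is worded around unanticipated events, while the harms the protocol itself thinks possible with this device are named in advance and so are anticipated. Read literally, the cases most relevant to the ring's safety are the ones the committee need not be shown.

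This is a pre-market study whose overall objective includes safety. After Day 56, subjects who found the ring helpful are asked to lengthen wear by 1-4 days where possible. Nothing requires the committee to have seen skin events or withdrawals before subjects reach that step. At stake is whether a run of reactions or skin-related withdrawals would be put before the people able to act on it while the trial is still running.

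**Working it through.** No arithmetic applies. The plan gives no expected rate for any listed harm, no review schedule and no threshold, so there is no figure to reproduce. The check is a reading of the whole document for any route from a listed harm to the committee.

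1. **The review duty.** The committee's task is stated once: "who will review any unanticipated adverse events". No other review duty, listing or meeting schedule appears.

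2. **The stopping power.** The committee members also "have the authority to stop the trial at any time if any safety concerns are raised". This half of the sentence is not confined to unanticipated events. It does not say who must raise a concern, on what information, or when.

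3. **Which harms are anticipated.** The document does not define the term. On its ordinary meaning, a type of event that the protocol names beforehand as a possible side effect is anticipated. That covers allergic reaction and skin worsening. Longer change time is also listed, but it is a burden more than a safety harm, and the Analysis plan already covers it through mean minutes per care session. The point does not rest on it.

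4. **Where these harms are recorded, and whether the text sends them on.**

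| Place in the document | What is captured | Sent to the committee? |
|---|---|---|
| Safety section, skin-score rule | Withdrawal at a score of 3 or more without a known cause | Not stated |
| Safety section, reaction rule | Removal for an allergic or suspected adverse reaction | Not stated |
| Visits One to Three | Skin assessment by the investigator | Not stated |
| Visit Three | Side effects reported by the subject | Not stated |
| Secondary Outcomes | Skin condition; adverse event counts | Not stated |
| Analysis plan | Skin condition at study visits; no line for adverse events | Not stated |

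5. **Other bodies that could stop the trial.** None is named. The recruitment paragraph before the Inclusion Criteria withholds study results from the sponsor until the statistical analysis has been completed independently. It does not say whether adverse event reports count as results, so the sponsor cannot be assumed to be a second line of review.

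6. **Putting these together.** A subject with a listed harm is removed under step 4. The event is anticipated under step 3, so step 1 does not require it to be reviewed. Step 2 lets the committee act only if someone brings the matter forward, and no one is told to. The data for aggregate review are already collected; the instruction to pass them on is missing.

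**The case against.** The strongest reply is that the sentence has two halves and the second is broad. A cluster of skin withdrawals is plainly a safety concern, and the committee may stop the trial for one. This stands in part: a reader might infer that the committee is barred from considering listed harms, and the text does not support that. But authority to act on a concern is not a duty to be shown the data that would prompt one.

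A second reply is that the meaning of unanticipated is open. The risk list names types of event, without severity or frequency, so an unusually severe or frequent reaction might count as unanticipated. So might a high skin score without a known cause, which is the withdrawal trigger itself. This also stands. It makes the wording ambiguous where it could be plain, which is itself a reason to revise it.

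A third reply is that listed harms are managed. Affected subjects leave the trial and are clinically assessed as indicated, visits are in person, side effects are asked about, and one research team in one health system would see withdrawals build up among 30 subjects. A reader might infer that subjects are left unprotected or that harms would go unnoticed; the documents support neither. What remains is that passing a pattern to the committee is left to the team's discretion.

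Finally, how much a two-person committee should see in a small study of an external device is partly a matter of proportion. That is fair, and it limits both the weight of the point and the size of the remedy.

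**Conclusion.** The point holds in a limited form. As written, allergic reactions to the ring, worsening of the peristomal skin, and the withdrawals that follow can accumulate without required review by the only body the document names with authority to stop the trial. The shortfall is in aggregate oversight, not in the care of individual subjects.

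It would go too far to say that the stated rule defeats its own purpose, since the stopping power reaches any safety concern that is raised.

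The conclusion rests on two readings: that a listed side effect is an anticipated one, and that the single stated review duty is the full duty. A separate committee charter, if one exists, could change the second; the document mentions none. No event rate is assumed, because the conclusion does not depend on one. This is a cheap improvement, and it does not threaten the trial's primary comparison.

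**What to change.** In Safety Assessments and Termination Guidelines, replace the clause "who will review any unanticipated adverse events" with wording to this effect: the committee will review all adverse events, anticipated or not, and all withdrawals for skin score or suspected reaction, listed by period (with and without the ring). Continued ring use after Day 56 belongs in the with-ring listing. Leave the stopping authority as it is.

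Listing by period matters because each subject has 28 days without the ring before using it, so the committee can set the two side by side. How often the listing is sent is for the sponsor and the committee to settle. No stopping threshold or clinical rule is proposed.

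The cost is one sentence and a short listing for the existing two members, drawn from information the trial already collects. The only downside is the time they spend reading it.

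### Adverse events other than skin damage and leakage are solicited only after the ring period, and control-period appliance concerns need not reach the trial record, so the with/without-ring comparison of adverse events is at risk of bias

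*Combined protocol and SAP*

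**What the plan says.** Safety is part of the primary objective (Overall Objective). Secondary Outcomes, item 2, is "The number and frequency of adverse events". The Analysis plan opens with "All means and frequencies will be compared between the groups with the Osto Ring™ versus the group without it". Adverse events are not in the itemised list that follows, but an outcome expressed as a frequency falls under that general sentence. No adverse-event definition, log or collection window is given.

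The visit schedule (Study Design) provides the following:

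- **Visit One**, start of the control period: skin assessment, quality-of-life questionnaire and instructions for the diary: "They will be given Ostomy Evaluation Record [See appendix A] and asked to complete this at every pouching system change". No side-effect question is listed.
- **Visit Two**, end of the control period and start of the ring period: skin assessment, quality-of-life questionnaire, two records to complete at each change, and ring fitting ("They will be fitted for the proper Osto-Ring size and given a belt"). No side-effect question is listed.
- **Visit Three**, Day 56: subjects are asked to "report any side effects they may have experienced even if they do not think it is related to the Osto-Ring™". No look-back period is stated.

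Under Safety Assessments and Termination Guidelines, the paragraph on the Hollister system says "Concerns regarding this system will be handled by the regular physician", followed by "However, all concerns will be addressed". The same section removes from the trial any patient with an allergic reaction to either product or a suspected adverse reaction of any kind.

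**The concern.** A within-subject comparison of adverse events is interpretable only if an event has the same chance of being recorded in each period. Here the ring period ends with a prompted, all-cause question and the control period does not. During the control period the Hollister system is the only appliance worn, so any concern about the appliance falls under the sentence that gives its handling to the regular physician. Nothing requires that physician or the subject to pass the concern to the study team.

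If fewer control-period events are recorded, a ring with no effect on harms will appear to add some. In a pre-market study with safety in its primary objective, that would be a misleading result, and it would run against the device.

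**Working it through.** The plan gives no event rate, capture rate or calculation for adverse events, so there is no figure of its own to reproduce on this point. The check is a comparison of what each period captures, followed by an illustration on assumed inputs.

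**Step 1. Capture by period**

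| Source | Control period | Ring period |
|---|---|---|
| Ostomy Evaluation Record at each change (skin damage, odor, leakage; Appendix A) | Yes | Yes |
| Skin score at the visits that open and close the period (Appendix B) | Days 0 and 28 | Days 28 and 56 |
| Removal for a reaction to either product | Yes | Yes |
| Ring record with an item on problems (Appendix D) | No | Yes |
| All-cause side-effect question at the closing visit | No (Visit Two) | Yes (Visit Three) |
| Report-back of concerns handled by the regular physician | Not required | Not required |

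The first three rows are symmetric and cover the most foreseeable appliance harms. Rows four and five are not. The last row is the same for both periods in wording but not in effect: in the ring period the Day 56 question can pick up an event managed elsewhere, and in the control period no matching question does so. What remains exposed is mainly other or unsolicited events, such as pain or bleeding, for which Appendix A has no item.

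**Step 2. Size, on assumed inputs**

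Let p be the true risk per subject of such an event, equal in both periods. Let r be the fraction recorded in the ring period and c the fraction recorded in the control period. The false difference is p·r − p·c = p(r − c). With full ring-period capture (r = 1) it is p(1 − c), and the apparent risk ratio is 1/c. Enrolment is 30 subjects (Research Design), so the expected recorded counts are 30p with the ring and 30pc without.

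| p | c | Recorded, ring | Recorded, control | False excess (points) | Apparent ratio |
|---|---|---|---|---|---|
| 10% | 75% | 3 | 2.25 | 2.5 | 1.33 |
| 10% | 50% | 3 | 1.5 | 5 | 2.0 |
| 10% | 25% | 3 | 0.75 | 7.5 | 4.0 |
| 20% | 75% | 6 | 4.5 | 5 | 1.33 |
| 20% | 50% | 6 | 3 | 10 | 2.0 |
| 20% | 25% | 6 | 1.5 | 15 | 4.0 |
| 30% | 75% | 9 | 6.75 | 7.5 | 1.33 |
| 30% | 50% | 9 | 4.5 | 15 | 2.0 |
| 30% | 25% | 9 | 2.25 | 22.5 | 4.0 |

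Example: p = 20%, c = 50% gives 0.20 × (1 − 0.50) = 0.10. When c = r there is no bias.

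**Step 3. Chance of a false significant excess**

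The plan names no test for adverse events, so I used a paired exact (McNemar) test: n = 30, two-sided 5%, periods independent, r = 1. A subject is recorded with the event in the ring period only with probability p(1 − pc), and in the control period only with probability pc(1 − p). At p = 20% the chance of a significant result against the ring is 1.1% at c = 100%, 9.6% at c = 50% and 24.7% at c = 25%. At p = 10% it is 2.0% at c = 50% and 3.9% at c = 25%.

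**The case against.** The strongest reply is that the sentence on the regular physician says who provides care for a standard product and nothing about what is recorded. It also goes by product, not by period, since the Hollister system is worn throughout. That stands. A reader might infer that the protocol has a rule excluding Hollister-attributed events from the trial data; the documents contain no such rule. They are silent on recording, and the asymmetry comes chiefly from the question that is present at Visit Three and absent at Visit Two.

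A reader might also infer that ring harm blamed on the Hollister system would be lost, so that the bias could run either way. The Day 56 question is asked regardless of perceived cause, so the label does not decide capture there. The likely direction is one way, against the ring.

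Nor does the text support saying that control-period harms in general escape the trial. Skin damage and leakage enter the data in both periods whoever treats them, and a reaction leading to removal is necessarily known to the study team. The Day 56 question has no stated window, so it may also reach back into the control period, though with longer recall.

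What survives is narrower. The assurance that all concerns will be addressed, the site team's option to manage stoma concerns and the removal rule govern care and withdrawal. None of them says that a control-period event of another kind is recorded.

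**Conclusion.** The concern holds in a limited form. As written, control-period capture of adverse events other than skin damage and leakage is likely to be less complete than ring-period capture, so the with/without-ring comparison of adverse-event frequency is at risk of bias, most likely to the ring's disadvantage. It would go too far to call the comparison biased as a fact or impossible to interpret: adverse events are a secondary outcome, their comparison is inferred from a general sentence, and the main foreseeable harms are captured symmetrically.

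The size cannot be derived from the documents. The 2.5 to 22.5 points in the illustration rest on assumed p (10% to 30%), assumed c (25% to 75%), full ring-period capture and equal true risk. Here p refers only to events not already captured symmetrically. Subjects must have used this system for at least 8 weeks and are excluded at a skin score of 3 or more, so nothing in the documents supports one value of p over another, and it could be low. The case for change rests on the asymmetry and the small cost of removing it.

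**What to change.** Leave clinical care and the role of the regular physician unchanged. Change the recording:

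1. At Visit Two (Day 28), ask the same all-cause side-effect question as at Visit Three, and state the windows: Days 0–27 at Visit Two, Days 28–55 at Visit Three. This alone removes most of the asymmetry.
2. Add a study adverse-event log. Suggested wording: *Any stoma, skin or appliance concern arising from Day 0 is entered on the log with its date of onset, whichever product is suspected and whoever manages it. Concerns managed by the regular physician are reported to the study team for entry.*
3. In the Analysis plan, add adverse events to the itemised list. Compare all-cause events assigned by onset date (ring on or off), and report relatedness to the ring or the Hollister system descriptively only.

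The cost is a few sentences in the protocol, one question at an existing visit and one log line per concern. The downside is slightly more recording and a higher reported control-period event count. No extra visits or patients are needed.
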